The proportion of time that the SUA level is < 6 mg/dL will be computed by taking the ratio between the time during which the SUA level remains < 6 mg/dL (if necessary, using the linear interpolation method) and the entire time interval within Treatment Periods 3 and 6.

Let T_1 be the total time interval in hours for Treatment Period 3 of which W_1 hours is the time interval during which SUA level is < 6 mg/dL. Similarly, for Treatment Period 6, assume T_2 is the total time interval in hours of which W_2 hours is the time interval during which SUA level is < 6 mg/dL. For a subject to be considered a responder, the proportion of time that the SUA level is < 6 mg/dL during Treatment Periods 3 and 6 must be at least 80%. The proportion of time that the SUA level is < 6 mg/dL, i.e., percentage of non-hyperuricemic time, is calculated using the following formula:

$$\text{Proportion} = \frac{W_1 + W_2}{T_1 + T_2} \times 100$$

A logistic regression model controlling for the distribution of baseline characteristics will be performed as supportive analysis.

Summary tables of the percentage of responder (subjects who achieve and maintain reduction of SUA < 6 mg/dL for at least 80% of the time) in each treatment period will be provided by treatment group. Additionally, a summary table with the total time a subject has SUA values < 6 mg/dL will be provided for each treatment period by treatment group.

Summary tables of the actual values and change from baseline for SUA results will be provided for each scheduled sampling time point by treatment group.

Additionally, mean SUA level, reduction in mean SUA and percent reduction in mean SUA from baseline during Treatment Period 3 or Treatment Period 6 will be presented by treatment group.

- Mean SUA level is defined as the area under the SUA time curve (computed using the linear trapezoidal rule during Treatment Periods 3 and 6) divided by the corresponding time interval.
- Reduction in mean SUA is computed by subtracting baseline SUA level from mean SUA during Treatment Period 3 and 6.
- Percent reduction in the mean SUA from baseline is computed as the mean SUA level during Treatment Periods 3 and 6 minus baseline SUA level divided by baseline SUA level multiplied by 100

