13.4.2 Secondary Efficacy Endpoints and Analyses

The secondary endpoints of this study are:

- Comparison in the percentage of patients on SEL-212 vs. KRYSTEXXA who achieve and maintain reduction of SUA < 6 mg/dL for at least 80% of the time during Treatment Period 6
- Comparison in the percentage of patients on SEL-212 vs. KRYSTEXXA who achieve and maintain reduction of SUA < 6 mg/dL for 100% of the time during Treatment Period 6
- Comparison in the percentage of patients on SEL-212 vs. KRYSTEXXA who achieve and maintain reduction of SUA < 6 mg/dL for at least 80% of the time during Treatment Period 3
- Comparison in the percentage of patients on SEL-212 vs. KRYSTEXXA who achieve and maintain reduction of SUA < 6 mg/dL for 100% of the time during Treatment Period 3
- Comparison between patients on SEL-212 vs. KRYSTEXXA in pre-dose SUA values > 6 mg/dL during Treatment Periods 2-6. The pre-dose SUA is collected on the dosing day prior to the dosing administration or it is collected at the visit where dosing would have occurred had the patient not been previously withdrawn from study drug.
- Comparison between patients on SEL-212 vs. KRYSTEXXA of the change in health questionnaires
- Comparison between patients on SEL-212 vs. KRYSTEXXA of gout flare incidence per 3-month period (Treatment Periods 1-3 and Treatment Periods 4-6)
- Comparison between patients on SEL-212 vs. KRYSTEXXA of gout flare frequency per 3-month period (Treatment Periods 1-3 and Treatment Periods 4-6)
- Comparison between patients on SEL-212 vs. KRYSTEXXA of the change from Baseline to Treatment Period 6 in number of tender joints
- Comparison between patients on SEL-212 vs. KRYSTEXXA of the change from Baseline to Treatment Period 6 in number of swollen joints

All statistical tests in secondary endpoints for the comparison between SEL-212 and KRYSTEXXA will be performed using one-sided tests at a type 1 error rate level of $\alpha=5\%$. In addition, 90% confidence intervals for treatment differences between SEL-212 and

KRYSTEXXA treatment groups will be computed. The efficacy analyses will be carried out based on the ITT and PP Sets. mITT analyses will be performed if appropriate.

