4.2. Secondary Efficacy Endpoints

Secondary Endpoints:

- Reduction of mean SUA in patients on SEL-212 vs. KRYSTEXXA® as computed by subtracting baseline SUA level from the mean SUA (area under the SUA time curve) during Treatment Period 3 and Treatment Period 6
- Percent reduction of mean SUA in patients on SEL-212 vs. KRYSTEXXA® as computed as the mean SUA level during treatment period (area under the SUA time curve) minus baseline SUA level divided by baseline SUA level multiplied by 100 during Treatment Period 3 and Treatment Period 6
- Percentage of patients on SEL-212 vs. KRYSTEXXA® who achieve and maintain reduction of SUA < 6 mg/dL for at least 80% of the time during Treatment Period 6
- Percentage of patients on SEL-212 vs. KRYSTEXXA® who achieve and maintain reduction of SUA < 6 mg/dL for 100% of the time during Treatment Period 6
- Reduction of mean SUA in patients on SEL-212 vs. KRYSTEXXA® as computed by subtracting baseline SUA level from the mean SUA (area under the SUA time curve) during Treatment Period 6
- Percent reduction of mean SUA in patients on SEL-212 vs. KRYSTEXXA® as computed as the mean SUA level during treatment period (area under the SUA time curve) minus baseline SUA level divided by baseline SUA level multiplied by 100 during Treatment Period 6
- Percentage of patients who achieve and maintain reduction of SUA < 6 mg/dL for at least 80% of the time during Treatment Period 3
- A summary table of the number and percentage of patients who achieve and maintain reduction of SUA < 6 mg/dL for 100% of the time during Treatment Period 3 will be provided by treatment group.
- Reduction of mean SUA in patients on SEL-212 vs. KRYSTEXXA® as computed by subtracting baseline SUA level from the mean SUA (area under the SUA time curve) during Treatment Period 3
- Percent reduction of mean SUA in patients on SEL-212 vs. KRYSTEXXA® as computed as the mean SUA level during treatment period (area under the SUA time curve) minus baseline SUA level divided by baseline SUA level multiplied by 100 during Treatment Period 3
- Percent of patients on SEL-212 vs. KRYSTEXXA® in pre-dose SUA values > 6 mg/dL during Treatment Periods 2-6. The pre-dose SUA is collected on the dosing day prior to the dosing administration or it is collected at the visit where dosing would have occurred had the patient not

This document is confidential.

Statistical Analysis Plan

Sponsor: Selecta Biosciences

Protocol No.: SEL-212/202

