The estimator for the comparison between the treatment groups is defined as the difference in the proportion of responders between patients receiving SEL-212 versus those receiving KRYSTEXXA® during Treatment Periods 3 and 6. The statistical testing will be performed confirmatory using the Cochran-Mantel-Haenszel (CMH) test – considering the randomization stratum of tophus presence (yes/no) – with a one-sided type 1 error rate $\alpha = 5\%$. In addition, 90% two-sided confidence intervals for the overall treatment difference between SEL-212 and KRYSTEXXA® treatment groups without stratification will be computed. The analysis of the estimands will be carried out based on the ITT primarily. Supportive analyses will be performed on the mITT and the PP.

A logistic regression model to compare treatment difference controlling for presence of tophus will be performed as supportive analysis.

In addition, a sensitivity analysis will be performed as below for the primary endpoint:

- If a subject withdraws from study treatment before completing period 6 due to stopping rules met for treatment, the subject will be considered as a non-responder for the primary efficacy endpoint.
- If a subject withdraws from the study before completing period 6 or the study terminates prior to a subject completing period 6, the primary efficacy endpoint is based on SUA assessment for period 3 where $T1$ be the total time interval in hours for Treatment Period 3 of which $W1$ hours is the time interval during which SUA level is < 6 mg/dL:

$$\text{Percentage (p)} = \frac{W1}{T1} \times 100$$

Summary tables of the percentage of responders (patients who achieve and maintain reduction of SUA < 6 mg/dL for at least 80% of the time) will be provided by treatment group. Additionally, a summary table with the total time a patient has SUA values < 6 mg/dL will be provided for treatment period 3 and treatment period 6 by treatment group.

Summary tables of the actual values and change from baseline for SUA results will be provided for each scheduled sampling time point by treatment group.

This document is confidential.

Additionally, mean SUA level, reduction in mean SUA and percent reduction in mean SUA from baseline during Treatment Periods 3 and 6, during Treatment 3, and during Treatment Period 6 will be summarized by treatment group respectively and will be compared for treatment difference using ANOVA model with presence of tophus and treatment group as fixed factors

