- Mean SUA level is defined as the area under the SUA time curve (computed using the linear trapezoidal rule during Treatment Periods 3 and 6) divided by the corresponding time interval.
- Reduction in mean SUA is computed by subtracting baseline SUA level from mean SUA during Treatment Period 3 and 6.
- Percent reduction in the mean SUA from baseline is computed as the mean SUA level during Treatment Periods 3 and 6 minus baseline SUA level divided by baseline SUA level multiplied by 100

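### The mean-SUA change endpoints are compared by ANOVA without baseline SUA, which probably costs a few percent of precision on three of six endpoints; the sign and sidedness of *reduction* also need stating

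*SAP*

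**What the plan says.** **Definitions.** SAP 7.1 states: "Reduction in mean SUA is computed by subtracting baseline SUA level from mean SUA during Treatment Period 3 and 6". The percentage version has the same sign: "Percent reduction in the mean SUA from baseline is computed as the mean SUA level during Treatment Periods 3 and 6 minus baseline SUA level". That difference is then expressed as a percentage of the baseline value. Protocol 13.4.1 carries the same formulas.

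**Status.** SAP 4.2 lists these measures as secondary endpoints ("Reduction of mean SUA in patients on SEL-212 vs. KRYSTEXXA® as computed by subtracting baseline SUA level from the mean SUA"). Reduction and percent reduction each appear for Treatment Periods 3 and 6 together, Period 6 alone and Period 3 alone, which makes six endpoints. The protocol gives them a lower status: in 13.4.1, "percent reduction in mean SUA from baseline during Treatment Period 3 or Treatment Period 6 will be presented by treatment group", and its list of secondary endpoints in 13.4.2 does not include them. SAP 7.4 does not record the change of status.

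**Model.** SAP 7.1 says that mean SUA level, reduction and percent reduction "will be compared for treatment difference using ANOVA model with presence of tophus and treatment group as fixed factors". It names no baseline covariate, sidedness or alternative.

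**Other change scores.** HAQ-DI (SAP 7.2.2), PrGA (7.2.3), SF-36 (7.2.4) and the joint counts (7.2.6) are analysed by ANCOVA with treatment, stratum and the baseline value.

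**Sidedness.** Protocol 13.4.2 has a general rule at the 5% level: "All statistical tests in secondary endpoints for the comparison between SEL-212 and KRYSTEXXA will be performed using one-sided tests". SAP 7.2.1 states one-sided 5% for four CMH endpoints, and mean SUA is not among them.

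**The concern.** The SAP treats SUA, the central measure of the trial, differently from its other change-from-baseline outcomes and gives no reason. ANOVA on a change score is ANCOVA with the baseline slope forced to 1. That suits patients who drift back to their own baseline. It does not suit responders, whose SUA should be low whatever their starting level. If the pooled slope is well below 1, the change score over-corrects and carries avoidable baseline variance into the error term. What is at stake is precision on secondary endpoints, which a value already in the record can improve.

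The label is a separate matter of clarity. By the formula, a true fall in SUA is a negative *reduction*, so the better arm has the smaller number. With neither sidedness nor direction written down, the reading of a one-sided result would be left to the programmer.

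**Working it through.** **1. The plan's own figure.** The documents give no calculation for mean SUA. The responder rates used below come from the primary sample size in SAP 3.5, which reproduces. With 65% vs 44%, one-sided 5% and 80% power, the mean rate is 0.545 and

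n = [1.645·√(2·0.545·0.455) + 0.842·√(0.65·0.35 + 0.44·0.56)]² / 0.21² = 68.5, rounded up to 69 per group.

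**2. Formula.** Let λ = SD(baseline) / SD(on-treatment mean SUA) and ρ = their within-arm correlation. The true slope is ρ/λ. In large samples

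Var(change-score ANOVA) / Var(ANCOVA) = (1 + λ² − 2ρλ)/(1 − ρ²) = 1 + (λ − ρ)²/(1 − ρ²).

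The ratio is 1 only when ρ = λ, that is, when the slope really is 1. Otherwise ANCOVA is more precise.

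**3. Range.** λ and ρ are assumptions.

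| λ | ρ = 0 | 0.2 | 0.3 | 0.5 |
|---|---|---|---|---|
| 0.25 | 1.06 | 1.00 | 1.00 | 1.08 |
| 0.4 | 1.16 | 1.04 | 1.01 | 1.01 |
| 0.6 | 1.36 | 1.17 | 1.10 | 1.01 |
| 1.0 | 2.00 | 1.67 | 1.54 | 1.33 |

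**4. Where the trial probably sits.** Assume responders average 1.3 mg/dL (the middle of 0.1–2.5) and non-responders 8.2 (baseline 8.7 less 0.5).
- Spread between the two groups alone: SD = (8.2 − 1.3)·√(0.545·0.455) = 3.44. A baseline SD of 1 to 2 then gives λ of at most 0.29 to 0.58.
- If only non-responders track baseline, the slope is about their average share, (35% + 56%)/2 = 0.455, so ρ ≈ 0.455λ.
- At λ = 0.29, ρ = 0.132 and the ratio is 1 + 0.158²/0.983 = 1.025, a saving of 2.5%.
- At λ = 0.58, ρ = 0.264 and the ratio is 1 + 0.316²/0.930 = 1.107, a saving of 9.7%.

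**5. Simulation.** 2,000 trials per row, 75 per arm, 65%/44% responders, baseline about 8.7 mg/dL floored at 7, responders uniform on 0.1–2.5, non-responders near baseline with noise SD 1, 1 and 1.5.

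| Baseline SD parameter | λ | ρ | ANOVA/ANCOVA variance, absolute | Saving (1 − 1/ratio) | Same ratio, percent reduction | Power, ANOVA vs ANCOVA (absolute) |
|---|---|---|---|---|---|---|
| 1.0 | 0.27 | 0.15 | 1.015 | 1.5% | 0.994 | 79.2% vs 79.6% |
| 1.5 | 0.36 | 0.20 | 1.034 | 3.3% | 0.993 | 78.6% vs 79.6% |
| 2.0 | 0.43 | 0.23 | 1.055 | 5.2% | 0.994 | 77.3% vs 78.3% |

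This is worth 75 × 0.015 = 1 to 75 × 0.055 = 4 patients per arm. Removing the floor, and letting non-responders return to 80–100% of baseline, widens the saving to about 1–15%. The floor is itself an assumption: 7 mg/dL is a Screening threshold (SAP 3.4.1), whereas baseline is the last value before the first infusion (SAP 5.8). Percent reduction gains nothing, because dividing by baseline already removes most of the dependence.

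**6. Sign.** A patient who falls from 9 to 2 mg/dL has a *reduction* of 2 − 9 = −7 and a *percent reduction* of −7/9 × 100 = −78%. If a tail were chosen from the label (upper tail, more reduction on SEL-212), a one-sided p of 0.01 would become 0.99. In the simulation that test rejected in 0% of trials, against 77–79% in the lower tail.

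**The case against.** The case for leaving the text alone is respectable. ANOVA with the stratum on a change score is valid and unbiased under randomisation. The likely loss is a few percent of variance and about one percentage point of power. The endpoints are secondary, SAP 7.2 sets no hierarchy, and neither the primary CMH test nor the sample size depends on them. All of this stands and limits the size of the point. It gives no reason for treating SUA differently from the other change scores when the covariate is already available.

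Three stronger readings are tempting, and the documents do not support them.

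- *The one-sided test looks in the wrong tail.* SAP 7.1 states no tail for this ANOVA, and an ordinary ANOVA F-test has no direction. The protocol's one-sided rule follows a list that omits mean SUA, so it applies only if carried over. The formula is explicit and the same in Protocol 13.4.1, SAP 4.2 and SAP 7.1, so anyone who follows it has a valid test. Harm arises only if the tail is taken from the label.
- *Chance imbalance in baseline SUA is left uncorrected.* Both change measures already contain baseline. The correction is made, with a slope fixed at 1 for the absolute measure. Only mean SUA level ignores baseline, and it is not one of the six listed endpoints.
- *All six endpoints lose precision.* The three percent-reduction endpoints do not, to any useful degree.

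**Conclusion.** The point holds as an inexpensive improvement. For the three absolute-reduction endpoints, ANCOVA with baseline SUA is the better analysis and matches the SAP's own practice. The variance saving is about 1–15%, most likely a few percent. That rests on an assumed baseline SD of 1 to 2 mg/dL, 65%/44% responders, and on-treatment SUA split between low values in responders and near-baseline values in non-responders. A larger loss (ratio 1.33 to 2.00 in the grid above) would need the baseline SD to equal the on-treatment SD, which that split makes unlikely. There is essentially no gain for percent reduction and no effect on the primary test.

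The sign is a labelling fault, and sidedness and favourable direction are unstated. Both need clarifying, but neither makes the planned analysis invalid.

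**What to change.** In SAP 7.1, replace the ANOVA by an ANCOVA with treatment, tophus stratum and baseline SUA. Use the same model for percent reduction for consistency, without expecting a gain. With baseline in the model, mean SUA level and absolute change give the same treatment estimate and test, so one of them can be dropped from testing.

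In SAP 4.2, SAP 7.1 and Protocol 13.4.1, either rename the measures change and percent change from baseline, or define them as baseline minus mean SUA. State in SAP 7.1 whether the test is one-sided at 5% (carrying over the rule in Protocol 13.4.2) or two-sided, and which sign of the difference favours SEL-212.

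The cost is a few lines of wording and no new data. It should be done before the endpoint results are calculated.

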7.2. Secondary Efficacy Endpoint Analyses

There is no hierarchical ordering of the secondary endpoints. All secondary endpoint will be included for analyses as described.

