7.7 Benefits and Risks

Chronic gout refractory to conventional therapy is a rare and serious condition associated with increased mortality rate and significantly decreased quality of life and for which there are very limited treatment options. Data from the Phase 2 study SEL-212/201 provide preliminary clinical evidence demonstrating that SEL-212 is a substantial improvement over available therapy:

- Substantially increased percentage of patients that maintain control of SUA while on therapy
- Substantially reduced gout flare rate during therapy
- Substantially reduced risk of infusion reactions
- More convenient to and greater compliance by patients because of once monthly therapy
- Acceptable safety at the doses to be studied in this Phase 2 study

SEL-212 has the potential to be an unprecedented safe and effective treatment option for patients for which other treatment options are inadequate. The overall balance between benefits and risks appears acceptable for the SEL-202/202 study of SEL-212 in the intended population of patients with chronic gout refractory to conventional therapy.

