13. STATISTICS

Details of the statistical methods outlined in the protocol for this study, including the hierarchical ordering of the secondary endpoints, will be documented in a Statistical Analysis Plan (SAP) that will be finalized prior to first patient randomized. The SAP may add additional exploratory analyses; modifications to the planned analyses will be identified as such in the SAP.

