13.4 Efficacy Analyses

13.4.1 Primary Efficacy Endpoint

The primary efficacy endpoint is defined as:

- Comparison in the percentage of patients on SEL-212 vs. KRYSTEXXA who achieve and maintain reduction of SUA < 6 mg/dL for at least 80% of the time during Treatment Period 3 and Treatment Period 6

The primary estimand will take into consideration the treatment policy strategy, ie, Treatment Period 6 (and also Treatment Period 3) assessments will be considered for all subjects in ITT independently whether the subject has completed the study treatment or has terminated early the study treatment. Additionally, the estimand based on the while-on-treatment strategy for dealing with study treatment terminators will be defined. For all used estimands of the primary efficacy, the estimator for the comparison between the treatment groups is defined as the difference in the proportion of responders between subjects receiving SEL-212 versus those receiving KRYSTEXXA during Treatment Periods 3 and 6. The statistical testing will be performed confirmatory using the Cochran-Mantel-Haenszel (CMH) test – considering the randomization

stratum of tophus presence (yes/no) – with a one-sided type 1 error rate $\alpha = 5\%$. In addition, 90% two-sided confidence intervals for the overall treatment difference between SEL-212 and KRYSTEXXA treatment groups without stratification will be computed. The analysis of the estimands will be carried out based on the ITT primarily. Supportive analyses will be performed on the mITT and the PP. For each defined estimand sensitivity analyses will be performed using different imputation approaches for missing values. Details of the applied approaches will be presented in the Statistical Analysis Plan.

The SUA time curve will be used to estimate the proportion of time that the SUA level is below 6 mg/dL. Based on the serum samples collected during Treatment Periods 3 and 6, an estimate of the time with SUA < 6 mg/dL can be determined by connecting each two neighboring data points with a straight line. If the SUA time curve goes above 6 mg/dL the linear interpolation method will be used to estimate the point in time at which the SUA time curve intercepts the line between the last SUA value < 6 mg/dL and the first value ≥ 6 mg/dL.

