7.4. Deviation from Analyses Planned in Protocol

7.4.1. Additional analyses

The following analyses are added even though they are not included in the protocol:

- Interim analysis.
- Subgroup analyses on the secondary endpoint by patient's primary efficacy endpoint (responder vs. non-responder).

The following analyses have been added as a result of the impact of Covid-19 on the study which may result in a larger anticipated number of subjects not completing the study and therefore not undergoing the assessments required for the primary efficacy endpoint or the study being stopped prematurely by sponsor decision. This is in line with FDA Guidance on Conduct of Clinical Trials of Medical Products during COVID-19 Pandemic Guidance for Industry, Investigators, and Institutional Review Boards.

- Additional analyses suggested to primary endpoint as sensitivity analyses to determine if the impact that these have on the conclusions of the study and to describe the impact of Covid-19 on the study performance.
- A sensitivity analysis which limited the analysis to results processed in the central laboratory to determine if this resulted in different conclusions to those found from the full analysis to determine consistency in laboratory testing between central and local laboratories.
- Kaplan-Meier analysis of withdrawal from study by treatment arm and presence of tophus to determine if subjects withdraw from the study in different proportions and at different rates within the treatment groups and depending on the presence of tophus.
- Kaplan-Meier analysis of withdrawal from study due to an adverse event by treatment arm and presence of tophus to determine if subjects experience adverse events in different proportions and at different rates within the treatment groups and depending on the presence of tophus.
- Poisson regression with number of gout flares experienced during treatment periods 1-6 as the dependent variable, treatment and the presence of tophus as independent variables and length of follow up as a covariate. The ITT population would be used to conduct this analysis. Similar analysis is done for periods 4-6.

This document is confidential.

8. Safety

The population used for safety analyses will be the Safety Set (SS). Safety will be assessed on the basis of adverse event (AE), clinical laboratory data, ECG parameters, physical examinations, and vital signs.

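### The protocol promises an ordered hierarchy of secondary endpoints; SAP 7.2 says there is none, SAP 7.4 does not record the change, and neither document says secondary p-values are nominal

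*SAP*

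**What the plan says.** **Hierarchy.** Protocol section 13, repeated in the synopsis under Statistical Methods, says that details, "including the hierarchical ordering of the secondary endpoints, will be documented in a Statistical Analysis Plan (SAP"), and that "modifications to the planned analyses will be identified as such in the SAP". SAP 7.2 opens with "There is no hierarchical ordering of the secondary endpoints" and adds only that all of them will be analysed. SAP 7.4.1 introduces its list with "The following analyses are added even though they are not included in the protocol". That list contains additions, and the hierarchy is not among them.

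**Level and status.** Protocol 13.4.2 says that all secondary comparisons "will be performed using one-sided tests at a type 1 error rate level of" 5%. SAP 7.2.1 repeats that level for four SUA endpoints and tests them in the same way as the primary. For the primary alone, protocol 13.4.1 and SAP 7.1 say: "The statistical testing will be performed confirmatory using the Cochran-Mantel-Haenszel (CMH) test". Protocol 7.7 describes the trial in passing: "Acceptable safety at the doses to be studied in this Phase 2 study".

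**Endpoint lists.** Protocol 6.2.2 has 8 secondary endpoints, the synopsis and protocol 13.4.2 have 10, and SAP 4.2 has 16. Six of the SAP's items are mean-SUA measures, beginning with "Reduction of mean SUA in patients on SEL-212".

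**The concern.** A hierarchy is a device for formal secondary testing: it fixes which results may be claimed, in what order, and when testing stops. The protocol says one will exist. The SAP withdraws it and puts nothing in its place: no gate, no adjustment, and no statement that the p-values are descriptive. The protocol's own rule that modifications be identified as such is not met either.

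What is at stake is the use made of secondary results. Someone holding the protocol could treat a secondary p-value below one-sided 5% as support for a claim, while someone holding the SAP could treat the same value as descriptive. That should be settled before results are seen.

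**Working it through.** **1. Text against text.**

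| Item | Protocol | SAP | Listed in SAP 7.4? |
|---|---|---|---|
| Order of secondary endpoints | To be given in the SAP (synopsis, 13) | None (7.2) | No |
| Six mean-SUA measures | Presented by group (13.4.1) | Secondary endpoints (4.2), tested by ANOVA (7.1) | No |
| SUA below 6 mg/dL for 100% of Treatment Period 3 | Treatment comparison (synopsis, 13.4.2) | Summary table only (4.2, 7.2.1) | No |
| Gate on primary, multiplicity adjustment, or nominal label | None | None | – |

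The six mean-SUA measures are reduction and percent reduction over three windows (Periods 3 and 6 together, Period 6, Period 3): 2 × 3 = 6. For the 100% endpoint in Period 3, the detailed CMH paragraphs of protocol 13.4.2 do not name it. The CMH method comes from the synopsis (Secondary Efficacy Analyses), which applies it to the SUA secondary endpoints generally. Protocol 13.4.2 supports a test through its general sentence on secondary comparisons.

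**2. The plan's own figure.** The documents give no error rate for the secondary family. Their one related calculation is the primary sample size: 65% vs 44%, one-sided 5%, 80% power, 69 per group. With mean rate 0.545,

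n = [1.645 × √(2 × 0.545 × 0.455) + 0.842 × √(0.65 × 0.35 + 0.44 × 0.56)]² / 0.21² = 68.5, rounded up to 69.

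This reproduces. By the same approximation, power is 80.3% at 69 and 83.1% at the 75 per group to be randomized.

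**3. Size of the secondary family.** Two counts come straight from the documents:

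- k = 4: the CMH tests listed in SAP 7.2.1 (80% in Period 3, 80% in Period 6, 100% in Period 6, pre-dose SUA above 6 mg/dL).
- k = 10: the endpoints in protocol 13.4.2, at one test each. This is a simplification, because some items hold several scores or windows.

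Suppose that no secondary effect exists and each test is at one-sided 5%.

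- Expected false positives, whatever the correlation, are 0.05 × k: 0.2 and 0.5.
- At least one, if independent, is 1 − 0.95^k: 1 − 0.95^4 = 18.5% and 1 − 0.95^10 = 40.1%.
- At least one, with an assumed common correlation ρ between normal test statistics, is 1 − ∫ Φ[(1.645 − √ρ·x)/√(1 − ρ)]^k φ(x) dx:

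| ρ (assumed) | k = 4 | k = 10 |
|---|---|---|
| 0 | 18.5% | 40.1% |
| 0.3 | 16.4% | 30.7% |
| 0.5 | 14.4% | 24.7% |
| 0.9 | 8.8% | 11.5% |

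The documents give no correlation. The endpoints are measured in the same patients and several are built from the same SUA curve, so the row for ρ = 0 is an upper reference and not an estimate for this trial. Every value is above 5%.

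**The case against.** The strongest reply is that the status is not really open. One test is called confirmatory, the secondaries have no gate and no order, and the protocol calls the trial Phase 2. On that reading secondary p-values are descriptive and the error rates above have no confirmatory consequence. Most of this stands: it is the natural reading. It remains an inference, however, and it conflicts with a protocol that still promises a hierarchy.

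Second, nothing is hidden. SAP 7.2 reverses the promise openly, where a reader would look, and the protocol does not say in which SAP section a modification must appear. That also stands. What is missing is the label: 7.2 states a position without identifying it as a change.

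Third, the protocol lets the SAP add exploratory analyses, so testing mean SUA is allowed. The fault is narrower: the six measures are called secondary endpoints and are not listed as additions.

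A reader might be tempted further than the documents go:

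- *That the primary result is compromised.* It is a single test at its own 5%, and nothing done with the secondaries changes that.
- *That the false-positive risk is far larger.* Counting every questionnaire score gives a much longer list; the SF-36 alone has 8 domain and 2 component scores, at two time points. Such a count is the reader's own construction and is dominated by closely related scores from one instrument, so an independence calculation on it would mislead.
- *That SAP 7.4 misleads because it lists a Poisson flare model already in protocol 13.4.2.* That is harmless over-disclosure.

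**Conclusion.** The point holds as a contradiction between the current texts. The protocol commits the SAP to a hierarchy and to identifying modifications; the SAP has no hierarchy and does not identify its absence as a change. Two smaller departures are also unlisted: the six added mean-SUA endpoints, and the dropped comparison for 100% control in Period 3.

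The consequence is limited to what may be claimed from secondary results. If each were read as a claim at one-sided 5%, the chance of at least one false positive would be between 8.8% and 18.5% for the four SUA tests, and between about 11.5% and 40.1% for ten endpoints. These ranges rest on no true secondary effect, one test per endpoint, and an assumed common correlation from 0.9 down to 0. If the secondaries are declared nominal, these figures have no confirmatory consequence. The documents do not support saying that the status cannot be worked out at all. They support saying that it is left to inference, against a protocol sentence that points the other way.

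**What to change.** **Preferred.**

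- In SAP 7.2, state that only the primary test is confirmatory and that all secondary p-values are nominal.
- In SAP 7.4, list the dropped hierarchy and the six mean-SUA additions as changes from the protocol.
- Restore the CMH test for 100% control in Treatment Period 3, or list its removal in SAP 7.4.
- At the next protocol amendment, correct the hierarchy sentence in the synopsis and section 13, and align the 6.2.2 list with 13.4.2. Without this the protocol would go on promising a hierarchy.

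The cost is a few sentences of SAP text, plus protocol wording that needs investigator signature and IRB approval under protocol 15.3 and can wait for the next amendment. Restoring the Period 3 test adds one test on data already collected. No secondary result could then be claimed as confirmatory.

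**Alternative, only if the sponsor wants secondary claims.** After a significant primary test, use a fixed sequence at one-sided 5% each, stopping at the first failure. The order must be fixed before the primary and secondary endpoints are calculated; SAP 2.2 holds that calculation back until the sponsor requests it or last dosing has occurred. The sequence should be limited to SUA endpoints whose post-dose values the sponsor has not seen. Flare endpoints stay nominal, because flares are collected as TEAEs (protocol 11.2.1) in a trial where sponsor personnel know the assignments (protocol 7.6.1). All other tests outside the sequence are also nominal. The sample size does not change. The cost is that nothing secondary can be claimed if the primary fails (the gate opens with about 83% probability at the planned rates and 75 per group), and that every step after a failure is lost.
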